Eligible subjects will be randomized 1:1 to Treatment Arm 1 or Treatment Arm 2 to receive study drug for 48 weeks. Following Screening and Baseline/Day 1 Visits, subjects will return for study visits at Weeks: 2, 4, 8, 12, 16, 20, 24, 30, 36, 42 and 48. Subjects that participate in the OLE will return for visits at Weeks: 50, 52, 56, 60, 64, 72 and visits every 12 weeks thereafter. During the OLE, the maximum period of co-administration of ENTO with Cyclosporine, Tacrolimus or MMF should not exceed 3 months. Subjects who do not wish to participate in the OLE will have a 30-day Follow-Up visit after their week 48 visit.

NOTE for subjects receiving tacrolimus, cyclosporine or MMF:

For subjects receiving these medicines at enrolment and are continuing on these medicines, the blood levels of tacrolimus, cyclosporine or the active metabolite of MMF (MPA) will be monitored at Baseline/Day 1 (prior to starting ENTO or placebo-to-match [PTM]), on Day 2 or Day 3 and Day 6 or Day 7 after initiating ENTO or PTM, and at the end of Week 2 and Week 50 study visit. Beyond these time points, concentration monitoring for tacrolimus, and cyclosporine should follow the treating institution's protocol and therapeutic range for monitoring these medicines. For subjects who initiate these medicines while already receiving ENTO, concentration monitoring for tacrolimus, cyclosporine and MPA should follow the treating institution's protocol and therapeutic range for monitoring these medicines. When a concentration sample is taken at a local lab in accordance with the treating institution's protocol for monitoring these medications, a sample may also be requested for central lab analysis.

At Screening the NIH cGVHD Diagnosis and Staging Criteria (NCDSC) ([Appendix 3](#)) will be administered. At Baseline/Day1 and Weeks 4, 8, 12, 16, 20, 24, 30, 36, 42, 48, 56, 60, 64, 72, every 12 weeks thereafter and Early Study Drug Discontinuation (ESDD) the NCAA ([Appendix 5](#)), and the LSS ([Appendix 6](#)) will be administered. Serological screening for HIV antibody (Ab), hepatitis B antigen, hepatitis C Antibody will be collected at the Screening visit. For subjects with hematologic malignancy, assessments of residual disease will be followed per the institutional guidelines.

Blood and urine will be collected at all study visits per the schedule of assessments (Table 6-1).

Blood for selected biomarkers will be collected at all study visits per the Schedule of Assessments (Table 6-1).

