6.5.2. Early Study Drug Discontinuation (ESDD)

If the subject discontinues study drug prior to the end of study, the subject will be asked to return to the clinic within 72 hours of stopping study drug for the Early Study Drug Discontinuation Visit. The subject will be asked to continue attending the schedule study visits through Week 48. Subjects who ESDD will not be eligible for the OLE phase of the study.

At the ESDD visit, any evaluations showing abnormal results indicating that there is a possible or probable causal relationship with the study drug, should be repeated weekly (or as often as deemed prudent by the investigator) until the abnormality is resolved, returns to baseline, or is otherwise explained.

Evaluation listed in [Table 6-1](#) will be completed at the ESDD visit.

The following will be conducted at the ESDD: review of adverse events (AEs) and changes in concomitant medications, vital signs (including weight), complete physical exam, primary malignancy assessment (if applicable), blood for hematology, chemistry, metabolic panel, selected biomarkers and urine for: pregnancy test (if applicable), and urinalysis. The NCAA and LSS will be assessed.

PFTs will be required at ESDD: spirometry with bronchodilator and diffusing capacity of the lungs for carbon monoxide (DLCO).

6.6. 30 Day Follow-Up Visit

Subjects who complete through Week 48 visit and who do not wish to participate in the OLE phase of the study will return to the clinic 30 days after the completion of study drug for the 30-Day follow-up visit. Subjects who complete the OLE will return to the clinic 30 days after the completion of study drug for the 30-Day follow-up visit

Subjects who permanently discontinue study drug and refuse to continue in the study will be asked to return to the clinic 30 days after the completion of the ESDD visit for the 30-Day follow-up visit.

For the purpose of scheduling a 30-Day follow-up visit, a ± 5 days window may be used. [Table 6-1](#) lists all procedures to be completed at the 30-Day Follow-up visit.

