2.3. Final Analysis

Due to early termination of the study by sponsor for lack of efficacy based on the interim futility analysis results, the final analysis of the data will be performed after all enrolled subjects have finished their follow-up/early-termination visit after the last dose of study drug, outstanding data queries have been resolved or adjudicated as unresolvable, and data have been cleaned and finalized.

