6. EFFICACY ANALYSES

6.1. Definition of the Primary Efficacy Endpoint

The primary endpoint is BORR by 24 weeks, defined as the proportion of subjects who achieve a complete or partial overall response (CR or PR) as assessed by the NCAA (Appendix 3) within 24 weeks, in the setting of add-on therapy to systemic corticosteroids as part of first-line therapy for cGVHD.

At each assessment time point, organ-specific responses will be determined according to Appendix 2. An overall time point response across all involved organs will then be determined according to Table 3. The best overall response across all time points up to 24 weeks will be used to calculate BORR by 24 weeks.

Table 3. Criteria for time point response determination

Response Category	Response Criteria
Complete response (CR)	Resolution of all cGVHD manifestations in each organ or site as described in the NCAA organ response determination table
Partial response (PR)	Improvement of at least 1 organ or site, without progression in any other organ or site as described in the NCAA organ response determination table.
Stable disease (SD)	Neither sufficient improvement to qualify for a PR nor sufficient decline to qualify for a PD
Progressive disease (PD)* * A flare is defined as acute worsening of signs and symptoms in any organ or site that occurs at least 4 weeks after PR/CR is achieved, which lasts ≤ 4 weeks.	
 • Worsening of signs and symptoms in any organ or site as described in the NCAA organ response determination table, taking the baseline as reference. OR • Increase in systemic corticosteroid dose to ≥ baseline dose (1 mg/kg/day) OR • Initiation of systemic immunosuppressive therapy other than systemic corticosteroids

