6.4. Secondary Efficacy Endpoints

6.4.1. Definition of Secondary Efficacy Endpoints

The key secondary endpoints are:

- Change from baseline in the skin domain of the LSS at 24 weeks
- Change from baseline in the mouth domain of the LSS at 24 weeks
- Change from baseline in the eyes domain of the LSS at 24 weeks
- Change from baseline in the total score of the LSS at 24 Weeks

Other secondary endpoints include:

- Duration of response, defined as the time from the documentation of BORR to the documentation of PD as defined in [Table 3](#). Note that a flare does *not* constitute an end to response. A sensitivity analysis for DOR could consider a flare does constitute an end to response.
- Proportion of subjects who ever achieve at least 50% reduction in systemic corticosteroid dose relative to baseline, where % reduction is calculated as (systemic corticosteroid dose at 24 weeks – baseline systemic corticosteroid dose) / baseline systemic corticosteroid dose.
- Proportion of subjects who initiate second-line therapy for cGVHD, defined as receiving any therapy besides systemic corticosteroids or study drug for the treatment of cGVHD. Inhaled and topical steroids are not considered second-line therapy.
- Failure-free survival (FFS), defined as the time from randomization to the earliest of first documentation of systemic therapy change, non-relapse mortality, or recurrent malignancy

- Safety and tolerability of ENTO

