6.4.2. Analysis Methods for Secondary Efficacy Endpoints

The key secondary endpoints will be analyzed using a two sample z-test at week 24.

Other secondary endpoints will be analyzed as follows:

DOR and FFS will be analyzed using the Kaplan-Meier (KM) method and stratified logrank test. Kaplan-Meier summary statistics (median, 95% CI for median, and 25th, 75th percentiles) and number and percentage of events will be presented by treatment group. A stratified Cox proportional hazards model will be used to estimate the hazard ratio and corresponding 95% CI. A KM survival plot will also be provided. Data for subjects who do not experience an event will be censored at the date of last visit. DOR will be analyzed only on subjects who responded.

Proportion of subjects with at least 50% reduction in systemic corticosteroid dose relative to baseline and proportion of subjects who initiated a second-line therapy for cGVHD will be analyzed similarly to the primary endpoint.

Line plot of change from baseline in each domain and total of LSS will be done.

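### DOR is censored at the last visit, but the off-drug 30-Day Follow-up has no NCAA, so responders who end on it carry 25-35 days in which most organ-based PD cannot be documented

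*SAP*

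**What the plan says.** SAP 6.4.2 analyses DOR and FFS together by Kaplan-Meier, stratified log-rank and stratified Cox, under one censoring rule: "Data for subjects who do not experience an event will be censored at the date of last visit". Protocol 8.5.2 has the same rule. Neither limits it to visits with a response assessment.

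DOR is "defined as the time from the documentation of BORR to the documentation of PD as defined in" Table 3 (SAP 6.4.1). That table (SAP 6.1) gives three routes to PD. The first is organ worsening by the NCAA response table. The others come from medication records: a steroid increase to at least the baseline dose, and "Initiation of systemic immunosuppressive therapy other than systemic corticosteroids".

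The protocol synopsis lists the NCAA at baseline, Weeks 4 to 48, OLE visits from Week 56, "every 12 weeks thereafter and Early Study Drug Discontinuation (ESDD) the NCAA". The 30-Day Follow-up is not listed, and its cell is empty in the NCAA rows of protocol Table 6-1 and SAP Appendix 1. Protocol 6.6 says that Table 6-1 "lists all procedures to be completed at the 30-Day Follow-up visit".

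Under protocol 6.6 the visit applies to Week 48 completers "who do not wish to participate in the OLE phase of the study will return to the clinic 30 days after the completion of study" treatment, to OLE completers, and to subjects who stop drug and refuse to continue (for them, 30 days after the ESDD visit). On timing: "For the purpose of scheduling a 30-Day follow-up visit, a ± 5 days window may be used".

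SAP 2.3 states that, after sponsor termination, "the final analysis of the data will be performed after all enrolled subjects have finished their follow-up/early-termination visit after the last dose of study drug".

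**The concern.** Kaplan-Meier requires that a subject counted at risk could be seen to have the event. After the last NCAA that no longer holds for most organ-based progression. If the censoring date is the follow-up visit, the subject still counts in the denominator while the main route to an event is closed. This lowers the estimated PD hazard and lengthens DOR. The added interval is also the first month off study drug, so it says little about response on treatment.

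At stake are the Kaplan-Meier curve and median DOR, and the log-rank test and hazard ratio if more responders in one arm end on this visit. FFS does not have the problem: therapy change, death and relapse can be learned without an NCAA.

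**Working it through.** The plan gives no DOR median, event count or power, so there is no plan figure to reproduce.

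**Length of the interval.** 30 ± 5 days gives 25 to 35 days. For early refusers it runs from the ESDD visit. For Week 48 completers it runs from the end of study drug, taken here to coincide with the Week 48 visit.

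**Single subjects, no event, 30 days added:**

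| Response | Last NCAA | DOR at last NCAA | DOR at last visit | Increase |
|---|---|---|---|---|
| Week 4 | Week 48 | 336 − 28 = 308 d | 338 d | 9.7% |
| Week 24 | Week 48 | 336 − 168 = 168 d | 198 d | 17.9% |
| Week 4 | ESDD, Week 8 | 56 − 28 = 28 d | 58 d | 107% |

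**Effect on the median.** Assumptions, none from the documents: DOR exponential with median 24 weeks, so h = ln 2 / 24 = 0.0289 per week; time from response to last NCAA uniform over 0-40 weeks; d = 30/7 = 4.29 weeks added; a share s of responders would end on the 30-day visit; PD recorded without delay up to the last NCAA.

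If all PD is organ-based, the risk set at time t has two parts (up to a common factor):

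- still observable: A = (40 − t)·exp(−ht)
- carried but not observable: s·B, with B = ∫ exp(−hl) dl from t − d to t (lower limit 0 when t < d)

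Kaplan-Meier therefore estimates h·A/(A + sB). At t = 24, A = 16 × 0.5 = 8.00 and B = (0.566 − 0.500)/0.0289 = 2.28. The hazard is multiplied by 8.00/10.28 = 0.78 when s = 1, and by 8.00/8.57 = 0.93 when s = 0.25.

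If 70% of PD is organ-based, split h into h_o = 0.7h and h_m = 0.3h. Then B = exp(−h_m·t)·∫ exp(−h_o·l) dl over the same limits, and the estimated hazard is (hA + h_m·sB)/(A + sB). Integrating each hazard to ln 2 gives the median:

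| True median | Share affected | All PD organ-based | 70% organ-based |
|---|---|---|---|
| 24 wk | 100% | 28.4 | 26.7 |
| 24 wk | 50% | 26.1 | 25.4 |
| 24 wk | 25% | 25.0 | 24.7 |
| 16 wk | 100% | 18.2 | 17.4 |
| 16 wk | 25% | 16.5 | 16.4 |

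For a true 24-week median, the 24-week Kaplan-Meier estimate is 53-55% instead of 50% if all are affected, and about 51% if a quarter are.

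A simulation on the actual NCAA schedule (assumed true medians 120, 240 and 480 days, two thirds of PD organ-based, stopping either absent or with median 168 days, all stoppers refusing visits) gives 0-3 percentage points on the curve and a PD rate 2-9% too low.

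**Between arms.** Give both arms the same true PD hazard (median 240 days), with median stopping at 84 days in one and 336 in the other. If every stopper refuses visits, the PD rate ratio under last-visit censoring is 0.92 (two thirds organ-based) or 0.89 (all organ-based), against 0.99-1.01 under last-NCAA censoring. If 25% refuse, it is 1.00-1.01.

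**Checking the remedy.** Suppose event-free subjects are censored at the last NCAA but medication-based PD found later still counts. The bias then turns downward: with 70% organ-based PD and all affected, a true 24 weeks becomes about 23.0. Both kinds of PD need the same cut-off.

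**The case against.** Several points narrow the concern, and most stand.

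- A reader might infer that every responder who stops drug is credited with an extra month. Protocol 6.5.2 asks early stoppers to keep their scheduled visits, with NCAA, through Week 48. Only those who refuse go to the 30-day visit instead.
- For Week 48 completers the extra month may not be intended. Protocol 3.2 and 8.5.5 and SAP 1.2 describe DOR follow-up to 48 weeks. SAP Table 1 closes the Week 48 window at Day 343, whereas a follow-up visit falls at about Day 361-371 (336 + 25 to 35). This stands as a reasonable reading, but the cap is not in the censoring rule and does nothing for early refusers.
- It is tempting to say that nobody assesses the interval. That goes too far. Chemistry, a symptom-directed examination and concomitant medications are scheduled at the visit, liver response is defined by laboratory values, and an NCAA is requested when second-line therapy starts.
- A reader might infer from SAP 2.3 that termination made the pattern common. The documents give no count, and the early-termination visit could be the ESDD visit, which has the NCAA.
- DOR is an other secondary endpoint in responders only, and SAP 3.5 drops formal comparisons. That lowers the stakes. SAP 6.4.2 nevertheless keeps the median, log-rank test and hazard ratio for DOR.

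**Conclusion.** The point holds in a limited form. As written, the rule can place the DOR censoring date 25-35 days after the last NCAA, in a period when most organ-based PD cannot be documented. The resulting bias is upward. Its size is not known, because the documents do not say how many responders end on this visit. Under the stated exponential model with a true 24-week median, it is about 1 week or less if a quarter are affected and about 3-4 weeks if all are; the latter is the upper case.

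A distorted treatment comparison might also be inferred, but the documents do not establish one. It requires the pattern to differ by arm, and a clear shift appeared only with very unequal stopping and universal refusal of visits. The point deserves correction because the direction is known and the remedy is simple, not because it would change the trial's conclusion.

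**What to change.** In SAP 6.4.2 and protocol 8.5.2, separate the DOR rule from the FFS rule:

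- **DOR:** censor event-free responders at their last NCAA with an evaluable overall response on or before Week 48 (for example, within the Week 48 window ending Day 343). Count PD of any type in the primary DOR analysis only if it occurs on or before that date. Say that an unscheduled NCAA prompted by new therapy after the final scheduled or ESDD assessment does not move the cut-off, since that would bring back the downward bias shown above.
- **Sensitivity analysis:** add medication-based PD found after that date.
- **FFS:** keep censoring at the last visit.

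It would also help to report, by arm, how many event-free responders had a last visit later than their last NCAA.

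The cost is a few sentences and no new data, because NCAA dates are already collected. DOR follow-up becomes slightly shorter, and a few late medication-based PD events move to the sensitivity analysis. If the SAP is already final, its section 1 provides for recording the change in the CSR.

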1. INTRODUCTION

1.1. Background

1.1.1. Background on Chronic Graft Versus Host Disease

[figure not shown]
Chronic Graft Versus Host Disease (cGVHD) is a disease observed in recipients of allogeneic hematopoietic stem cells, where the new immune system is reconstituted without complete tolerance to the host and begins to attack multiple organ systems including eyes, skin, mucosa, lungs, gut, and liver. Classic acute GVHD (aGVHD) occurs in episodes with donor cell engraftment before 100 days post-transplant and is thought to be mediated by donor T cells. Acute GVHD is observed in 35-50% of patients receiving hematopoietic stem cell transplant (HCT) {[Jacobsohn et al 2007](#)}. Acute GVHD is a risk factor for developing cGVHD, but cGVHD can develop without history of aGVHD. Chronic GVHD occurs in 35-70% of patients receiving allogeneic transplants. In the U.S., the incidence of cGVHD is estimated at ~3000-5000 patients per year, with prevalence at approximately 10,000 {[Vigorito et al 2009](#)}. Initial therapy for cGVHD consists of high dose systemic corticosteroids, however 50 to 60% of patients fail to have a complete response to this line of therapy.

No agents are currently approved for cGVHD. A combination of calcineurin inhibitors, mTOR inhibitors and mycophenolate mofetil (MMF) are frequently added as second-line therapy with an initial response rate of 20-70% {[Flowers et al 2015](#)}. The majority of responses are not durable, and cGVHD is associated with a 5-year mortality of 30-50% {[Blazar et al 2012](#)}. Current immunosuppressive treatments also increase the rate of life-threatening infections and cancer relapse due to presumably the loss of graft versus tumor effect. The absence of effective therapies is attributed to the limited understanding of disease pathophysiology and limited directed development by industry.

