8.1.3. Secondary Endpoint

The key secondary endpoints are:

- Change from baseline in the skin domain of the LSS at 24 weeks
- Change from baseline in the mouth domain of the LSS at 24 weeks
- Change from baseline in the eyes domain of the LSS at 24 weeks
- Change from baseline in the total score of the LSS at 24 Weeks

Other secondary endpoints include:

- DOR, defined as the time from the documentation of BORR to the documentation of PD as defined in Table 8-1. Note that a flare does *not* constitute an end to response.
- Proportion of subjects who achieve at least 50% reduction in systemic corticosteroid dose relative to baseline, where % reduction is calculated as (systemic corticosteroid dose at 24 weeks – baseline systemic corticosteroid dose) / baseline systemic corticosteroid dose
- Proportion of subjects who initiate second-line therapy for cGVHD, defined as receiving any therapy besides systemic corticosteroids or study drug for the treatment of cGVHD. Inhaled and topical steroids are not considered second-line therapy.
- Failure-free survival (FFS), defined as the time from randomization to the earliest of first documentation of systemic therapy change, nonrelapse mortality, or recurrent malignancy
- Safety and tolerability of ENTO

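### Duration of response ends only at documented PD, so responders who die without it are censored and the curve overstates the proportion alive and still in response

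*SAP*

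**What the plan says.** SAP 6.4.1 measures DOR as "the time from the documentation of BORR to the documentation of PD". Protocol 8.1.3 matches: "DOR, defined as the time from the documentation of BORR to the documentation of PD as defined in Table 8-1".

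PD is a composite of three components (SAP Table 3; protocol Table 8-1):

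- organ worsening, which the SAP words as "Worsening of signs and symptoms in any organ or site as described in the NCAA organ response determination table, taking the baseline as reference"
- a rise in systemic corticosteroid dose to the baseline level or above
- "Initiation of systemic immunosuppressive therapy other than systemic corticosteroids"

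The two tables take different reference points for organ worsening, but neither lists death.

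For DOR and failure-free survival (FFS) together, SAP 6.4.2 states "Data for subjects who do not experience an event will be censored at the date of last visit". Protocol 8.5.2 has the same rule. The methods are Kaplan-Meier, a stratified logrank test and a stratified Cox model, and DOR is restricted to responders. The only DOR sensitivity analysis named (SAP 6.4.1) concerns flares.

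FFS, in contrast, counts non-relapse mortality and recurrent malignancy as events. Protocol 1.1.1 says that "cGVHD is associated with a 5-year mortality of 30-50" percent.

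**The concern.** Kaplan-Meier treats a censored subject as someone who stays at risk and could still progress later. A subject who died in response cannot. Censoring that subject at the last visit removes a response that has ended and lets the remaining responders stand in for it. The result describes durability in a hypothetical setting without death. A reader of a DOR median will take it as time alive and responding.

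Visit spacing adds to this. NCAA assessments are 4 weeks apart to Week 24 and 6 weeks apart to Week 48. A responder who worsens and dies between two visits may have no documented PD and is censored at the earlier visit.

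Protocol 1.5 describes the drug as immunomodulatory and names serious infection as an event of interest. If it raised the number of infectious deaths among responders, DOR would not register them. SAP 2.2 also names DOR among the data the DMC weighs when the predictive probability of success is 30% or less.

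**Working it through.** **Reading the text.** Censoring of deaths is not stated in words. It follows from two clauses: the only event is documented PD, and everyone without an event is censored at the last visit. No visible text makes an exception. SAP 6.6 is redacted, and nothing is inferred from it.

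**Plan's own figure.** The documents give no DOR assumption, so there is nothing to reproduce on this point. The only computed design figure, 75% power for BORR, reproduces at 74.9% by exact enumeration but has no bearing on DOR.

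**Inputs.**

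- 5-year mortality of 30-50%, from protocol 1.1.1.
- Death hazard h, assumed constant over 260 weeks: −ln(0.70)/260 = 0.00137 per week and −ln(0.50)/260 = 0.00267 per week.
- PD hazard λ = 0.02 per week. This is an assumption, as the documents give none.

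**At 24 weeks after response.**

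- Deaths censored: exp(−24 × 0.02) = 0.619. Median ln 2/0.02 = 34.7 weeks.
- Death as an event, 30% mortality: exp(−24 × 0.02137) = 0.599. Median ln 2/0.02137 = 32.4 weeks.
- Death as an event, 50% mortality: exp(−24 × 0.02267) = 0.580. Median ln 2/0.02267 = 30.6 weeks.

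The overstatement is 2.0 to 3.8 percentage points at 24 weeks, and 2.3 to 4.1 weeks on the median.

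**Over the longest DOR follow-up.** A first response at Week 4 followed to Week 48 gives 44 weeks. The death risk is then 1 − exp(−44h) = 5.9% to 11.1%. With the 44-week PD risk varied as an assumption:

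| Assumed PD risk | Deaths censored | PD or death, 30% mortality | PD or death, 50% mortality |
|---|---|---|---|
| 20% | 80.0% | 75.3% | 71.1% |
| 40% | 60.0% | 56.5% | 53.4% |
| 60% | 40.0% | 37.7% | 35.6% |

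The gap runs from 2.3 to 8.9 points. It is largest when progression is rare. A simulation of the 40% PD, 50% mortality case gave 53.3%, against 53.4% by formula. For reference, λ = 0.02 corresponds to a 44-week PD risk of 1 − exp(−0.88) = 58.5%, close to the last row.

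**Between arms.** Assume equal 44-week PD risk of 40%, and death risks of 10% and 5%. With deaths censored the hazard ratio is 1.00. With death counted it is (0.511 + 0.105)/(0.511 + 0.051) = 1.10. The difference in deaths is invisible to the analysis as planned.

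**The case against.** Several points on the other side have force.

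- **Estimand.** With deaths censored, the logrank test and Cox model still compare cause-specific hazards of PD validly. This stands. What is lost is the reading of the curve and median as alive and in response.
- **Deaths are visible elsewhere.** FFS counts non-relapse deaths, SAP 7.1.6 tabulates all deaths by arm, and SAP 7.1.7 summarises CMV, EBV and PJP events. Excess infectious deaths would not go unseen. But FFS runs from randomization in all subjects, so it does not correct a responder-only DOR curve.
- **PD is broad.** Responders who need steroid escalation or new systemic immunosuppression before dying already count as events. This reduces the number affected.
- **Low stakes.** DOR is a non-key secondary endpoint outside the testing sequence. The study was stopped for lack of efficacy (SAP 2.3), and SAP 3.5 plans no formal comparisons. With 50 planned per arm and 50-80% responding, there are 25-40 responders; at 5.9-11.1% risk that is roughly 1-4 deaths per arm, before removing those who progress first. With 30 responders and an estimate near 60%, the standard error is about √(0.6 × 0.4/30) = 9 points, larger than most of the shifts above. This stands as to weight. But SAP 6.4.2 still reports the median, curve and hazard ratio, and the bias has a known direction.

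A reader might go further and infer that the rule rewards an arm with more early deaths by lengthening its DOR. The plan does not support that. Under constant, independent hazards the deaths-censored curve is exp(−0.02t) whatever the death hazard, so extra deaths leave it unchanged. Lengthening would also require that those who die were likelier to progress, and nothing in the documents establishes this.

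A reader might also assume a larger death hazard. At 0.005 per week, 5-year mortality would be 1 − exp(−1.3) = 73%, outside the protocol's range.

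**Conclusion.** The concern holds. Followed as written, the plan censors responders who die without documented PD. It therefore overstates the proportion alive and still in response, and it does not penalise an arm with more such deaths.

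At the assumed PD hazard, the overstatement is about 2-4 percentage points at 24 weeks and about 2-4 weeks on the median. Across the assumed PD risks at 44 weeks it is about 2-9 points. These figures rest on constant, independent hazards, on PD rates that the documents do not give, and on a mortality figure for cGVHD in general. Mortality among responders before PD may well be lower, which would shrink the effect.

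This is a correction worth making to a descriptive secondary endpoint. It does not touch the primary analysis.

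**What to change.** In SAP 6.4.1, define the DOR event as documented PD or death from any cause, whichever comes first, with death counted at the date of death. In 6.4.2, limit censoring at last visit to responders alive without PD. Align protocol 8.1.3 and 8.5.2.

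Keep the protocol-defined time to PD as a supportive analysis, using cumulative incidence with death as a competing event, and report the number of deaths in response by arm.

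The change would come after the futility interim, so the CSR should record it, with its date and reason. SAP section 1 already provides for documenting later changes there.

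The cost is small. FFS already needs deaths to be captured, so no new data collection should be required; the work is a few lines of text in two documents and one supportive table. The downsides are a slightly shorter DOR and a definition that departs from the protocol after the interim. Showing both analyses side by side lets the reader judge the effect of that departure.
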